1.1 Document Scope

This statistical analysis plan (SAP) covers the reporting of the trial progress and planned effectiveness analyses of the CPIT III trial. Analyses relating to health economic or qualitative data or any further exploratory post-hoc analyses are not covered by this SAP.

1.2 Glossary

AE	Adverse event
BMI	Body mass index
CACE	Complier average causal effect
CI	Chief Investigator
CO	Chemical symbol for carbon monoxide
CONSORT	Consolidated Standards of Reporting Trials
DMEC	Data Monitoring and Ethics Committee
EDD	Estimated Date of Delivery
FTND	Fagerström Test for Nicotine Dependence
IMD	Index of Multiple Deprivation
LSOA	Lower-layer Super Output Areas
NHS	National Health Service
NRT	Nicotine replacement therapy
PIS	Patient information sheet
ppm	Parts per million
REC	Research Ethics Committee
SAE	Serious adverse event
SQD	Set quit date
SOP	Standard operating procedure
SSS	Stop Smoking Service(s)
TCC	Trial Contact Centre
TMG	Trial Management Group
TSC	Trial Steering Committee
YTU	York Trials Unit

1.3 Procedural Documentation

1.3.1 Standard Operating Procedures

The following YTU SOPs and guidance documents will apply to the conduct and documentation of the CPIT III trial analysis:

S01	Statistical Considerations	Latest version: 5.0
SG02	Statistical Reporting Guidance	Latest version: 3.0

1.3.2 Associated Documentation

Appropriate YTU standard forms apply. Any assumptions made during the processing and merging of data as well as for the analysis will be documented (internal document reference numbers in bracket) using a Trial Assumptions Form (F23). In the event of necessary changes or additions to analyses detailed here, these will be documented on a Statistical Analysis Plan Departure Form (F24). The statistical analysis will be signed off using a Primary Analysis Sign-off Form (F16) and Statistical Quality Assurance Checklist (C03).

2 Trial Summary

The following sections give a summary of the CPIT III trial. Full details are given in the Study Protocol (latest version 4.0, dated 11/03/2020) and the published trial protocol paper [1].

2.1 Objectives

2.1.1 Primary Objective

The primary objective was to assess whether offering financial incentives in addition to usual Stop Smoking Service (SSS) support to pregnant smokers was effective in increasing the smoking cessation rate at late pregnancy.

2.1.2 Secondary Objectives

The secondary objectives were:

- To compare quit rates at four weeks post quit date between women offered incentives and those receiving usual SSS care only
- To compare quit rates at six months after birth (point abstinence) and until six months after birth (continuous abstinence) between women offered incentives and those receiving usual SSS care only
- To assess the cost effectiveness of financial incentives
- To identify the effects of differences in SSS, maternity care and demographic diversity of pregnant smokers on the effectiveness, cost effectiveness and transferability of financial voucher incentives

2.2 Design

CPIT III is a phase III, pragmatic, multi-centre, randomised controlled trial of the offer of financial incentives added to usual SSS care to engage with SSS and quit smoking versus usual care alone. In addition, economic and process evaluations were embedded in the study.

2.3 Intervention

2.3.1 Original intervention

The intervention was composed of several stages, each of which involved the offer of a financial incentive in the form of a Love2shop gift voucher, delivered via registered post.

The first stage of the intervention was designed to encourage participants to engage with SSS, while the remaining stages were designed to encourage participants to quit smoking and remain abstinent.

At the first stage, if the participant attended an appointment with the SSS and set a date on which they would quit smoking, they received a gift voucher with a value of £50.

At the second stage, the smoking status of those participants who engaged with SSS and set a quit date was obtained from the SSS at four weeks post-quit date. Smoking status was ascertained by asking the participant the question:

1. Have you smoked (even a puff) in the last two weeks?

Participants who answered 'No' were contacted by a research nurse to arrange an appointment to obtain a Carbon Monoxide (CO) breath test reading, where this had not already been collected by the SSS. Participants who had a CO reading less than or equal to the accepted threshold for their site received a gift voucher with a value of £50. Table 1 gives details of the CO threshold for each site.

Table 1: CO threshold for each site

Site	CO threshold (<=ppm)
Lanarkshire	4
Belfast	3
Salisbury	4
Poole	4
Isle of Wight	5
Dorchester	4
Portsmouth	4

At the third stage, the smoking status of those participants, who met the criteria to receive a shopping voucher at the second stage, was obtained from the SSS (where available) or by a research nurse at 12-weeks post quit date. Smoking status was obtained by asking the participant the question:

1. Have you smoked at all since your one-month follow-up?

Participants who answered 'No' were contacted by a research nurse to arrange an appointment to provide a CO breath test reading, where this had not already been collected by the SSS. Participants who had a CO reading less than or equal to the accepted threshold for their site received a gift voucher with a value of £100.

At the fourth stage, participants were contacted by the trial team at a random date between 34 and 38 weeks gestation, regardless of whether or not they met the criteria for the previous shopping vouchers. The participants were asked the following questions:

- 1. Have you smoked at all in the last eight weeks?
- 2. If yes, have you smoked more than five cigarettes in total in the last 8 weeks?

If the participant answered 'No' to the first question, or 'Yes' to the first question and 'No' to the second question, they were contacted by a research nurse to arrange an appointment to obtain a CO reading. Participants who had a CO reading less than or equal to the accepted threshold for their site had to provide a saliva sample and once the saliva sample was collected/received, they were sent a gift voucher with a value of £200.

2.3.2 Changes to the intervention in response to the Covid-19 pandemic

Due to the Covid-19 pandemic, SSS were disrupted. As a result, on the 16th of March 2020 the following changes were made for the intervention group:

- Participants who received SSS behavioural support and set a quit date via telephone (where this would have previously been conducted face-to-face) were considered to have engaged with the SSS, and received a gift voucher with the value of £50.
- Participants who self-reported as having quit with no CO verification at the 4-week follow-up received a gift voucher with the value of £50.
- Participants who self-reported as having quit at the 4-week follow-up were contacted at the 12 week follow-up. If they self-reported as quit with no CO verification at the 12-week follow-up they were sent a gift voucher with the value of £100.
- Participants who self-reported as having quit at the primary outcome stage in late pregnancy and for whom a saliva sample was received by the trial team were sent a gift voucher with the value of £200.

2.4 Usual care

Stop smoking support is freely available to pregnant women throughout the UK. Models of support differ however depending on where women live. In general, two main types of support are offered which can be described as 'specialist' (just for pregnant women) or 'generic' (for all smokers including pregnant women). Within this framework, support offered commonly includes: (1) individual/group support provided by specially trained advisers who may be nurses, or midwives, (2) support provided in hospital setting, women's homes or other mutually acceptable venue, (3) at least one face-to-face counselling session with follow-up support, often by telephone, to 12 weeks after a quit date is set, and (4) advice on use of NRT utilising various models of prescribing (e.g. nurse/GP prescribing/pharmacy).

The National Institute of Health and Care Excellence (NICE) - PH26 Smoking: stopping in pregnancy and after childbirth published comprehensive guidance in 2010 regarding services that should be provided to pregnant smokers (National Institute for Health and Care Excellence. Quitting smoking in pregnancy and following childbirth. 2010. https://www.nice.org.uk/guidance/ph26).

2.5 Outcomes

2.5.1 Primary Outcome

The primary outcome is cotinine/anabasine verified abstinence from smoking for at least 8 weeks towards the end of pregnancy. All participants were contacted by the Trial Team at a random date between 34 and 38 weeks gestation and asked the following questions:

- 1. Have you smoked at all in the last eight weeks?
- 2. If yes, have you smoked more than five cigarettes in total in the last 8 weeks?

If the participant answered 'No' to the first question, or 'Yes' to the first question and 'No' to the second question, they were contacted by a research nurse to arrange an appointment to biochemically verify their smoking status. Participants were asked to provide a CO reading and a saliva sample (or urine sample when saliva collection could not be tolerated), which was tested for cotinine in the first instance. Where the cotinine result was less than or equal to the threshold (Table 2) and the participant had not reported any NRT/e-cigarette use then the participant was defined as a biochemically verified non-smoker.

Participants who indicated current NRT/e-cigarette use and had a saliva cotinine result < 10ng/ml were defined as biochemically verified non-smokers. Where participants indicated current NRT/e-cigarette use and the saliva cotinine result was \geq 10ng/ml, saliva samples were also tested for anabasine. Where the anabasine result was less than or equal to the threshold 0.2ng/ml and the saliva cotinine result was \geq 10ng/ml then the participant was defined as a biochemically verified non-smoker.

Urine samples were also collected from participants who indicated NRT/e-cigarette to allow further assaying in the event of any dubiety. At present however there is no defined threshold for anabasine in urine and a judgement regarding smoking status would need to be taken by the Research team in conjunction with advice from ABS Labs in this scenario.

Table 2: Thresholds for cotinine samples in saliva

Cotinine threshold, ng/ml	
Saliva	10.0
Urine	50.0
Plasma	10.0

2.5.2 Secondary Outcomes

2.5.2.1 Engagement with SSS (Locally Defined) and Setting of Quit Date Before 26 weeks Gestation

A participant was defined to have engaged with SSS if they had attended an appointment with a smoking cessation advisor (face-to-face or by telephone) and agreed a quit date before reaching 26 weeks gestation (calculated using the estimated delivery date and the antenatal booking appointment date).

2.5.2.2 CO-validated abstinence from smoking for at least 14 days at four weeks after quit date

At the four-week stage, participants were asked the following question:

• Have you smoked (even a puff) in the last two weeks?

If the participant answered 'Yes' to this question, they were defined as a self-reported smoker at the four week time point, and if the participant answered 'No' they were defined as a self-reported non-smoker. Participants who provided a CO result less than or equal to the CO threshold for their site were defined as CO-validated non-smokers. Participants whose four-week follow-up was due after the 16th of March 2020 were not able to provide CO samples due to restrictions implemented in response to the Covid-19 pandemic.

2.5.2.3 Cotinine/anabasine verified self-reported point abstinence from smoking for at least 8 weeks at 6 months post-partum

At the 6 months post EDD stage, participants were asked the following question:

Have you smoked at all in the past eight weeks?

If the participant answered 'No' to this question, they were defined as a self-reported nonsmoker at the six months post EDD stage. If the participant answered 'Yes', they were asked a second question:

Have you smoked more than five cigarettes in total in the last eight weeks?

If the participant answered 'No' to this question, they were defined as a self-reported nonsmoker. If the participant answered 'Yes', they were defined as a self-reported smoker.

If a participant was defined as a self-reported non-smoker, they were asked to provide a CO reading, and a saliva/urine sample in order for their smoking status to be biochemically verified. The sample was tested for cotinine and a participant defined as a biochemically verified non-smoker where the result was less than or equal to the threshold (Table 2) and the participant had not reported any NRT/e-cigarette use.

Participants who indicated current NRT/e-cigarette use and had a saliva cotinine result < 10ng/ml were defined as biochemically verified non-smokers. Where participants indicated current NRT/e-cigarette use and the saliva cotinine result was \geq 10ng/ml, saliva samples were also tested for anabasine. Where the anabasine result was less than or equal to the threshold 0.2ng/ml and the saliva cotinine result was \geq 10ng/ml then the participant was defined as a biochemically verified non-smoker.

2.5.2.4 Cotinine/anabasine verified self-reported continuous abstinence from smoking from late pregnancy to 6 months post-partum

At the 6 months post EDD stage, participants were asked the following question:

Have you smoked since your baby was born?

If the participant answered 'No' to this question, they were defined as a self-reported continuous non-smoker at the six months post EDD stage. If the participant answered 'Yes', they were asked a second question:

• Have you smoked more than five cigarettes in total since your baby was born?

If the participant answered 'No' to this question, they were defined as a self-reported continuous non-smoker. If the participant answered 'Yes' they were defined as a self-reported continuous smoker.

If a participant was defined as a self-reported non-smoker, they were asked to provide a CO reading, and a saliva/urine sample in order for their smoking status to be biochemically verified. The sample was tested for cotinine and a participant defined as a biochemically verified non-smoker where the result was less than or equal to the threshold (Table 2) and the participant had not reported any NRT/e-cigarette use.

Where participants indicated current NRT/e-cigarette use and the saliva cotinine result was >= 10ng/ml saliva samples were also tested for anabasine. Where the anabasine result was less than or equal to the threshold 0.2ng/ml then the participant was defined as a biochemically verified non-smoker.

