2.9.5 Follow-up 5: Six months postpartum

Similar to the late pregnancy follow-up all women were contacted at six months after their expected delivery date to ascertain smoking status and collect a saliva/urine sample for those women who self-reported as quit. Quit status six months after birth was ascertained by two sets of questions:

1. 'Have you smoked in the last 8 weeks?' If yes 'Have you smoked more than 5 cigarettes in that time?', and 2. 'Have you smoked since your baby was born?' If yes, 'Have you smoked more than 5 cigarettes in total since your baby was born?'

Follow-up procedures (i.e. no. of contact attempts, data collection and saliva/urine sample collection and assay) were the same as those described for the late pregnancy follow-up. Biological samples of saliva and urine will not be available for use by other researchers.

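### Continuous abstinence is named as running from late pregnancy but is derived only from smoking since birth, and its verification rule omits low-cotinine NRT/e-cigarette users

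*SAP*

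**What the plan says.** The heading of SAP 2.5.2.4 is "Cotinine/anabasine verified self-reported continuous abstinence from smoking from late pregnancy to 6 months post-partum". The derivation below it starts with "Have you smoked since your baby was born", and the rule is: "If the participant answered 'No' to this question, they were defined as a self-reported continuous non-smoker at the six months post EDD stage". A woman who answers yes is then asked "Have you smoked more than five cigarettes in total since your baby was born", and a no to that also makes her a continuous non-smoker. Verification follows at the same contact: "If a participant was defined as a self-reported non-smoker, they were asked to provide a CO reading, and a saliva/urine sample".

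SAP 2.9.5 introduces the questions with "Quit status six months after birth was ascertained by two sets of questions". One set covers the last eight weeks and the other covers the time since birth. It also says "Similar to the late pregnancy follow-up all women were contacted at six months after their expected delivery date", so late-pregnancy status does not limit who is asked. SAP 4.5 analyses the outcome with the covariates and assumptions of the primary model and adds no late-pregnancy condition. Table 5 reports it with its own adjusted odds ratio and p-value.

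On verification, SAP 2.5.2.3 (point abstinence at the same follow-up) contains this rule: "Participants who indicated current NRT/e-cigarette use and had a saliva cotinine result < 10ng/ml were defined as biochemically verified non-smokers". SAP 2.5.1 has the same rule for the primary outcome. SAP 2.5.2.4 does not.

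**The concern.** The name fixes an interval that opens in late pregnancy, but nothing in the derivation looks at late pregnancy. A woman who was smoking at 34-38 weeks, stopped at delivery and passes the post-partum test is a failure on the primary outcome. She is nevertheless a success on an outcome whose stated interval begins at that time point. The same can happen to a woman with no late-pregnancy data, whom SAP 4.4 counts as smoking.

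Anyone reading Table 5 by the outcome's name would take the row to describe women who were abstinent in late pregnancy and remained so. Events from women who stopped at delivery would be mixed in. If their share is similar in the two arms, the relative effect is diluted. If it differs, the estimate could move either way.

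The omitted cotinine clause is a separate flaw in the same section. Read literally, it lets a nicotine user with higher cotinine and low anabasine be verified, while one with lower cotinine has no rule that verifies her.

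**Working it through.** **1. Label against derivation.** Apply the written rules to women who report no smoking, or at most five cigarettes, since birth and whose post-partum sample is verified negative:

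| Status at 34-38 weeks | Primary outcome (2.5.1, 4.4) | Continuous abstinence as derived (2.5.2.4) | Agrees with the 2.5.2.4 heading? |
|---|---|---|---|
| Verified non-smoker | Success | Success | Yes, except that no question covers the time from that contact to birth |
| Smoker | Failure | Success | No |
| Missing | Failure (assumed smoking) | Success | Not established |

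The second and third rows are the defect. Late-pregnancy status is collected (Table 3, Follow-up 4) but not used here.

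**2. Verification routes.** For a saliva sample from a self-reported non-smoker:

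| NRT/e-cigarette use | Cotinine, ng/ml | Anabasine, ng/ml | 2.5.1 and 2.5.2.3 | 2.5.2.4 |
|---|---|---|---|---|
| No | at or below 10 | not needed | Verified | Verified |
| Yes | below 10 | not needed | Verified | No rule |
| Yes | 10 or more | at or below 0.2 | Verified | Verified |

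One sample can therefore verify a woman for point abstinence and leave her unclassified for continuous abstinence.

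**3. The plan's own figure.** The SAP states no rate, power or sample size for continuous abstinence. The only figure to reproduce is that for the primary outcome (2.6: 7% v 14%, 90% power, 15% loss; 4.1: two-sided 5%).

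- n per arm = [1.960 × √(2 × 0.105 × 0.895) + 1.282 × √(0.07 × 0.93 + 0.14 × 0.86)]² / 0.07² = 401.
- Allowing for loss: 401 / 0.85 = 472 per arm, or 944 in total, against 940 stated.
- With 470 × 0.85 = 399.5 per arm, power is 89.9%.

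The stated size reproduces, and the outcome definition in 2.5.2.4 plays no part in it.

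**4. Illustration of dilution (assumed rates).** Let a and b be the true continuous-abstinence rates in control and intervention. Take the SAP's planning rates of 7% and 14% as late-pregnancy success. Let q be the share of the remaining women in each arm who qualify only through stopping by delivery. Then:

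- control as derived = a + (1 − 0.07)q
- intervention as derived = b + (1 − 0.14)q

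With a = 3%, b = 6% and 470 per arm:

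| q | Control | Intervention | Odds ratio | Power |
|---|---|---|---|---|
| 0 | 3.00% | 6.00% | 2.06 | 60% |
| 1% | 3.93% | 6.86% | 1.80 | 51% |
| 3% | 5.79% | 8.58% | 1.53 | 38% |
| 5% | 7.65% | 10.30% | 1.39 | 30% |

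With a = 4% and b = 8%, the odds ratio goes from 2.09 (q = 0) to 1.48 (q = 5%), and power from 73% to 45%.

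The values of a, b and q are all assumptions, as is an equal q in both arms. The powers also use all 470 per arm, whereas SAP 4.5 excludes women followed up before six months (about 35%, by 2.9.5.1), so absolute power would be lower.

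**The case against.** The secondary objective in SAP 2.1.2 speaks only of continuous abstinence until six months after birth and gives no starting point. A reader might infer that the stated objective is to test whether the late-pregnancy effect persists, and that the derivation defeats it. The SAP does not say that. Against the objective as worded, a since-birth measure is legitimate and the heading is the faulty part. This stands, and it is why renaming is a full alternative to redefining.

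A reader might also infer that low-cotinine NRT or e-cigarette users are counted as smokers for this outcome. The text does not go that far. The smoking default in SAP 4.5 is for women whose smoking status is missing, and these women have both a self-report and a cotinine result. They are left unclassified. Since the same clause sits just above in 2.5.2.3 for the same contact, the omission is probably a drafting slip. It still needs correcting, because a programmer working from 2.5.2.4 alone would have no rule for them.

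It is also fair to say that the numbers of misclassified women may be small. Each must report at most five cigarettes since birth and pass a biochemical test. The SAP offers nothing with which to size this group, so the illustrative figures cannot support a high severity.

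Finally, data collection was to end on 31/10/2020 (2.9.5.1), SAP version 1.1 is dated 28 July 2021, and the statistician is not blinded (2.8). Redefining an outcome at that stage invites a charge of post-hoc choice. This bears on which remedy to prefer and does not remove the contradiction.

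**Conclusion.** The point holds as a should-fix on one secondary outcome. The heading and the derivation in SAP 2.5.2.4 describe different intervals, and no other section reconciles them. The protocol is not at hand and might add a late-pregnancy condition, but the SAP sets out a question-by-question derivation that contradicts its own heading. The missing cotinine clause is a second, smaller defect in the same section.

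The number of women affected cannot be found from the SAP. The fall in the odds ratio from 2.06 to between 1.80 and 1.39 shows only what dilution would look like under assumed rates of 3% v 6% and an equal share of 1% to 5% in each arm. An unequal share could bias the estimate in either direction. The primary outcome, the primary model and the sample size are unaffected.

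**What to change.** Choose one of two corrections for the interval and record the choice and its date in the SAP amendment log.

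- **Redefine.** Require verified non-smoker status on the primary outcome, in addition to the since-birth criteria and the negative post-partum sample. The inputs are already collected. The costs are fewer events and the carrying over of the missing-equals-smoking rule, so a woman missed in late pregnancy fails whatever her post-partum data show. The time from the late-pregnancy contact to birth is still covered by no question, and the SAP should say so.
- **Rename.** Keep the derivation, call the outcome *continuous abstinence from birth to 6 months post-partum* in 2.5.2.4 and Table 5, and cross-tabulate it by arm with the primary outcome, showing missing late-pregnancy status separately. This costs wording and one table. It also avoids a late change of definition by an unblinded team, but the outcome then says nothing by itself about persistence from late pregnancy.

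Under either choice, insert into 2.5.2.4 the clause already used in 2.5.1 and 2.5.2.3 for NRT/e-cigarette users with saliva cotinine below 10 ng/ml. That is one sentence and needs no new data.

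### The secondary outcome labelled continuous abstinence from late pregnancy is derived only from smoking since birth and a postpartum sample, so a late-pregnancy smoker can count as a success

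*SAP*

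**What the plan says.** The heading of SAP 2.5.2.4 describes biochemically verified "self-reported continuous abstinence from smoking from late pregnancy to 6 months post-partum". The derivation beneath it has three parts:

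- The first question, put at the six-month contact, is "Have you smoked since your baby was born". The rule for the answer is: "If the participant answered 'No' to this question, they were defined as a self-reported continuous non-smoker at the six months post EDD stage".
- A woman who answers yes is asked "Have you smoked more than five cigarettes in total since your baby was born". A no to this also makes her a continuous non-smoker.
- Verification follows from that answer: "If a participant was defined as a self-reported non-smoker, they were asked to provide a CO" reading and a saliva or urine sample, which is tested for cotinine and, for some users of NRT or e-cigarettes, anabasine.

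Section 2.9.5 repeats the same two questions. The secondary objective in 2.1.2 gives the end of the abstinence period but no start. Section 4.5 analyses the outcome with the covariates and assumptions of the primary model, counts missing status as smoking, and excludes women followed up before six months. Table 5 lists the outcome simply as continuous abstinence at six months.

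Late-pregnancy status is sought separately. Under 2.5.1 all participants are contacted at 34-38 weeks about the previous eight weeks, and reported quitting is verified on a sample. That is the primary outcome.

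**The concern.** The name claims a period that starts in late pregnancy, but the rule measures one that starts at birth. A programmer who follows 2.5.2.4 exactly would count as continuously abstinent a woman who smoked throughout pregnancy, stopped at delivery and tests negative at six months. The same woman would be a failure on the primary outcome and a success on an outcome whose title says she had not smoked since late pregnancy.

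The SAP already has a separate outcome for point abstinence at six months (2.5.2.3). A reader of the results will take the continuous outcome as showing how many late-pregnancy quits lasted. As derived, it mixes those women with women who stopped at delivery, and the reported rate and odds ratio would not describe what the label says.

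**Working it through.** **Periods covered, side by side**

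| Element | Period covered |
|---|---|
| Outcome name (2.5.2.4 heading) | Late pregnancy to six months postpartum |
| Both classifying questions (2.5.2.4, 2.9.5) | Birth to the postpartum contact |
| Verifying sample (2.5.2.4) | Taken after the postpartum self-report |
| Secondary objective (2.1.2) | Ends at six months after birth; no start given |
| Analysis (4.5) | Adds no late-pregnancy condition |
| Primary outcome questions (2.5.1) | Eight weeks before the 34-38 week contact; not used in 2.5.2.4 |

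Section 4.5 carries over the assumptions of the primary analysis. Those assumptions concern missing outcomes and missing covariates. They do not alter who meets the continuous-abstinence definition.

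**The plan's own figure.** The SAP gives no expected rate for this outcome. Its only planning figures are in 2.6: 7% v 14%, 90% power, 15% loss, 940 women. They reproduce. The usual two-proportion formula without continuity correction gives 401 per arm; 401/0.85 rounds up to 472 per arm, or 944 in total against the stated 940. They are used here only for the late-pregnancy rates.

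**Illustration of scale**

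- From the SAP: about 65% reached at six months as planned (2.9.5.1), so 0.65 × 940 = 611 women, or 305.5 per arm. Not quit in late pregnancy: 93% and 86% (from 7% and 14% in 2.6).
- Assumed, not in the SAP: true continuous abstinence of 3% (usual care) and 6% (incentives), and the same share x of late-pregnancy smokers in each arm who stop at birth and pass the postpartum test.
- Rates under the SAP rule: usual care 0.03 + 0.93x; incentives 0.06 + 0.86x.
- OR = [p₁/(1−p₁)] / [p₀/(1−p₀)], with p₁ the incentives rate and p₀ the usual-care rate. z = ln(OR) divided by the square root of the summed reciprocals of the four cell counts.

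| x | Usual care | Incentives | OR | z |
|---|---|---|---|---|
| 0% | 3.00% | 6.00% | 2.06 | 1.75 |
| 1% | 3.93% | 6.86% | 1.80 | 1.58 |
| 2% | 4.86% | 7.72% | 1.64 | 1.44 |
| 3% | 5.79% | 8.58% | 1.53 | 1.33 |

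**Second set of assumptions.** Suppose instead that half of the 7% and 14% late-pregnancy quitters stay abstinent. The rates with a late-pregnancy condition are then 3.5% v 7.0% (OR 2.08). Under the SAP rule the OR is 1.84, 1.69 or 1.44 for x of 1%, 2% or 5%. At 2%, late-pregnancy smokers make up 0.93 × 2% / 5.36% = 35% of usual-care successes and 0.86 × 2% / 8.72% = 20% of incentives successes.

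**Direction when the shares differ.** Return to the 3% v 6% case with x = 1% in usual care. The usual-care odds are 0.0393/0.9607 = 0.0409. To keep the OR at 2.06, the incentives odds must be 0.0409 × 2.064 = 0.0844, a rate of 7.79%. That needs a share of (7.79 − 6.00)/0.86 = 2.1% in the incentives arm. Above that share the OR is inflated, not diluted.

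**The case against.** Several counter-arguments have force.

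- **It is one secondary outcome.** The primary outcome is untouched, and the since-birth measure remains a valid randomised comparison under the wrong name. In the first illustration z is below 1.96 in every row, so no test result changes. This stands and limits the severity.
- **The size rests on assumptions.** No document figure bounds the share who stop at birth; if it is near zero, so is the effect. This stands for the size. The mismatch between name and rule does not depend on it.
- **A negative postpartum sample is also required.** True, but a sample taken months after delivery cannot show whether she smoked before it.
- **The fuller definition has its own bias.** Women not reached at 34-38 weeks become failures even if abstinent throughout. Section 2.6 allows 15% loss, and 2.9.4 is concerned about loss among controls in particular, which would push the odds ratio in favour of incentives. Counting missing as smoking is already the SAP's rule for the primary outcome (4.4), so the condition is consistent with the plan, but the direction of this bias has to be shown.
- **Timing.** The amendment log dates version 1.1 to 28 July 2021, data collection was due to end on 31/10/2020 (2.9.5.1), and the statistician is not blinded (2.8). Redefining an outcome then is more delicate than renaming it. This stands and is why relabelling is an acceptable minimum.

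A reader might also infer that the continuous rate will exceed the late-pregnancy quit rate. In the first illustration that needs x above (7 − 3)/0.93 = 4.3% in usual care and (14 − 6)/0.86 = 9.3% in incentives, both beyond the 1-3% used there. It is possible in principle but not shown. Nor do the documents establish that women who stop at birth owe nothing to the vouchers, so dilution cannot be taken as certain.

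**Conclusion.** The point holds as a mismatch between the name and the derivation of one secondary outcome. As written, the SAP allows a woman who fails the primary outcome to be reported as continuously abstinent from late pregnancy, and no other section prevents it. That conclusion needs no assumption.

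The effect on the estimate is conditional. With equal stop-at-birth shares of 1% to 3% and assumed true rates of 3% v 6%, the odds ratio falls from 2.06 to between 1.80 and 1.53. Unequal shares could reduce, cancel or reverse this. The documents do not support the stronger inference that the trial's main conclusion is at risk, or that the bias must run towards no effect. The point should be fixed before this outcome is reported, but it does not threaten the primary analysis.

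**What to change.** In 2.5.2.4, define continuous abstinence as all three of:

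1. verified non-smoker at the late-pregnancy primary outcome, with missing counted as smoking as in 4.4;
2. no more than five cigarettes since birth by self-report;
3. verified non-smoker at six months.

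State in the same place that neither set of questions covers the interval from the 34-38 week contact to delivery, so even this definition is not strictly continuous. If the present derivation is kept, report it as 'abstinence since birth'.

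If the sponsor prefers not to redefine an outcome after data collection, the minimum correction is to use that label in 2.5.2.4 and Table 5.

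The cost is SAP wording and one extra condition in the derivation, using late-pregnancy status that the trial already collects as its primary outcome. The fuller definition yields fewer events and counts women without a late-pregnancy result as not abstinent. Late-pregnancy loss to follow-up should therefore be shown by arm beside the result.
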